**Notes:**

1. Withhold or permanently discontinue pembrolizumab is at the discretion of the investigator or treating physician.
2. For subjects with Grade 3 or 4 immune-related endocrinopathy where withhold of pembrolizumab is required, pembrolizumab may be resumed when AE resolves to  $\leq$  Grade 2 and is controlled with hormonal replacement therapy or achieved metabolic control (in case of T1DM).

## 8.2 Dose modification and toxicity management of infusion-reactions related to pembrolizumab

Pembrolizumab may cause severe or life threatening infusion-reactions including severe hypersensitivity or anaphylaxis. Signs and symptoms usually develop during or shortly after drug infusion and generally resolve completely within 24 hours of completion of infusion. Dose modification and toxicity management guidelines on pembrolizumab associated infusion reaction are provided in Table 4.

**Table 4** Pembrolizumab Infusion Reaction Dose modification and Treatment Guidelines

NCI CTCAE Grade	Treatment	Premedication at Subsequent Dosing
Grade 1 Mild reaction; infusion interruption not indicated; intervention not indicated	Increase monitoring of vital signs as medically indicated until the subject is deemed medically stable in the opinion of the investigator.	None
Grade 2 Requires therapy or infusion interruption but responds promptly to symptomatic treatment (e.g., antihistamines, NSAIDs, narcotics, IV fluids); prophylactic medications indicated for $\leq$ 24 hrs	
Stop Infusion.
 
Additional appropriate medical therapy may include but is not limited to:
 
 
• IV fluids
 
• Antihistamines
 
• NSAIDs
 
• Acetaminophen
 
• Narcotics
 
 
Increase monitoring of vital signs as medically indicated until the subject is deemed medically stable in the opinion of the investigator.
 
If symptoms resolve within 1 hour of stopping drug infusion, the infusion may be restarted at
	
Subject may be premedicated 1.5h (<math>\pm</math> 30 minutes) prior to infusion of pembrolizumab with:
 
 
• Diphenhydramine 50 mg po (or equivalent dose of antihistamine).
 
• Acetaminophen 500-1000 mg po (or equivalent dose of analgesic).
 

	
50% of the original infusion rate (e.g. from 100 mL/hr to 50 mL/hr). Otherwise dosing will be held until symptoms resolve and the subject should be premedicated for the next scheduled dose.
 
Subjects who develop Grade 2 toxicity despite adequate premedication should be permanently discontinued from further study drug treatment
	
Grades 3 or 4 Grade 3: Prolonged (i.e., not rapidly responsive to symptomatic medication and/or brief interruption of infusion); recurrence of symptoms following initial improvement; hospitalization indicated for other clinical sequelae (e.g., renal impairment, pulmonary infiltrates) Grade 4: Life-threatening; pressor or ventilatory support indicated	
Stop Infusion.
 
Additional appropriate medical therapy may include but is not limited to:
 

• Epinephrine**

• IV fluids

• Antihistamines

• NSAIDs

• Acetaminophen

• Narcotics

• Oxygen

• Pressors

• Corticosteroids

 
Increase monitoring of vital signs as medically indicated until the subject is deemed medically stable in the opinion of the investigator. Hospitalization may be indicated. **In cases of anaphylaxis, epinephrine should be used immediately.
 
Subject is permanently discontinued from further study drug treatment.
	No subsequent dosing

Appropriate resuscitation equipment should be available at the bedside and a physician readily available during the period of drug administration.
 
For further information, please refer to the Common Terminology Criteria for Adverse Events v4.0 (CTCAE) at http://ctep.cancer.gov
		

### **8.3 Other allowed dose interruption for pembrolizumab**

Pembrolizumab may be interrupted for situations other than treatment-related AEs such as medical / surgical events or logistical reasons not related to study therapy. Subjects should be placed back on study therapy within 3 weeks of the scheduled interruption, unless otherwise discussed with the study sponsor (principal investigator). The reason for interruption should be documented in the patient's study record.

### **8.4 Diet/Activity/Other Considerations:**

#### **8.4.1 Diet**

Subjects should maintain a normal diet unless modifications are required to manage an AE such as diarrhea, nausea or vomiting.

### **8.4.2 Contraception**

Pembrolizumab may have adverse effects on a fetus in utero. Furthermore, it is not known if pembrolizumab has transient adverse effects on the composition of sperm.

For this trial, male subjects will be considered to be of non-reproductive potential if they have azoospermia (whether due to having had a vasectomy or due to an underlying medical condition).

Female subjects will be considered of non-reproductive potential if they are either:

(1) Postmenopausal (defined as at least 12 months with no menses without an alternative medical cause; in women < 45 years of age a high follicle stimulating hormone (FSH) level in the postmenopausal range may be used to confirm a post-menopausal state in women not using hormonal contraception or hormonal replacement therapy. In the absence of 12 months of amenorrhea, a single FSH measurement is insufficient.);

**OR**

(2) Have had a hysterectomy and/or bilateral oophorectomy, bilateral salpingectomy or bilateral tubal ligation/occlusion, at least 6 weeks prior to screening;

**OR**

(3) Has a congenital or acquired condition that prevents childbearing.

Female and male subjects of reproductive potential must agree to avoid becoming pregnant or impregnating a partner, respectively, while receiving study drug and for 120 days after the last dose of study drug by complying with one of the following:

(1) Practice abstinence† from heterosexual activity;

**OR**

(2) Use (or have their partner use) acceptable contraception during heterosexual activity.

Acceptable methods of contraception are‡:

Single method (one of the following is acceptable):

- Intrauterine device (IUD)
- Vasectomy of a female subject's male partner
- Contraceptive rod implanted into the skin

Combination method (requires use of two of the following):

- Diaphragm with spermicide (cannot be used in conjunction with cervical cap/spermicide)
- Cervical cap with spermicide (nulliparous women only)
- Contraceptive sponge (nulliparous women only)
- Male condom or female condom (cannot be used together)
- Hormonal contraceptive: oral contraceptive pill (estrogen/progestin pill or progestin-only pill), contraceptive skin patch, vaginal contraceptive ring, or subcutaneous contraceptive injection

†Abstinence (relative to heterosexual activity) can be used as the sole method of contraception if it is consistently employed as the subject's preferred and usual lifestyle and if considered acceptable by local regulatory agencies and ERCs/IRBs. Periodic abstinence (e.g., calendar, ovulation, sympto-thermal, post-ovulation methods, etc.) and withdrawal are not acceptable methods of contraception.

‡ If a contraceptive method listed above is restricted by local regulations/guidelines, then it does not qualify as an acceptable method of contraception for subjects participating at sites in this country/region.

Subjects should be informed that taking the study medication may involve unknown risks to the fetus (unborn baby) if pregnancy were to occur during the study. In order to participate in the study subjects of childbearing potential must adhere to the contraception requirement (described above) from the day of study medication initiation (or 14 days prior to the initiation of study medication for oral contraception) throughout the study period up to 120 days after the last dose of trial therapy. If there is any question that a subject of childbearing potential will not reliably comply with the requirements for contraception, that subject should not be entered into the study.

#### **8.4.3 Use in Pregnancy**

If a subject inadvertently becomes pregnant while on treatment with pembrolizumab, the subject will immediately be removed from the study. The site will contact the subject at least monthly and document the subject's status until the pregnancy has been completed or terminated. The outcome of the pregnancy will be reported to the Sponsor, IRB/DSMC and Merck without delay and within 24 hours to the Sponsor and DSMC and within 2 working days to Merck if the outcome is a serious adverse experience (e.g., death, abortion, congenital anomaly, or other disabling or life-threatening complication to the mother or newborn).

The study investigator will make every effort to obtain permission to follow the outcome of the pregnancy and report the condition of the fetus or newborn to the Sponsor. If a male subject impregnates his female partner the study personnel at the site must be informed immediately and the pregnancy reported to the Sponsor, IRB/ DSMC and Merck and followed as described above and in Section 16.8.

#### **8.4.4 Use in Nursing Women**

It is unknown whether pembrolizumab is excreted in human milk. Since many drugs are excreted in human milk, and because of the potential for serious adverse reactions in the nursing infant, subjects who are breast-feeding are not eligible for enrollment.

## 9 STUDY CALENDAR

**CYCLE** Calendar: 1 cycle = 21 days ( $\pm$  3 days)

Examination	Screening 	C1 	C2	C3	C4	C5	C6	C7 and beyond	End of Treatment	Follow-up 
Informed consent	X									
Medical history/baseline AE	X									
Eligibility criteria	X									
Vital signs	X	X	X	X	X	X	X	X	X	
Physical examination	X	X	X	X	X	X	X	X	X	X
ECOG performance status	X	X	X	X	X	X	X	X	X	
Hematology 	X	X	X	X	X	X	X	X	X	
Chemistry 	X	X	X	X	X	X	X	X	X	
Urinalysis	X								X	
T3, free T4, TSH 	X				X			X 		
PT, PTT, INR	X									
Pregnancy test 	X									
Review Adverse events and events of clinical interest		X	X	X	X	X	X	X	X	
Review of concomitant medications	X	X	X	X	X	X	X	X		
Archival tissue for PD-L1 analysis 	X									
Archival tissue for TMB analysis 	X									
Archival tissue for Ki-67 analysis 	X									
ECG 	X									
CT scans (c/a/p) 	X			X		X		X 	X	X 
Disease Assessment (irRECIST) 	X			X		X		X	X	X
MRI 										
Study drug 		X	X	X	X	X	X	X		

- 1 ALL Pre-study/Screening procedures should be completed within 4 weeks of study enrollment - with the exception of laboratory tests which need to be completed within 14 days prior to study enrollment.
- 2 Hematology includes CBC with differential and platelets
- 3 Chemistry includes Albumin, Alkaline Phosphatase, Aspartate Aminotransferase, Alanine Aminotransferase, Total Bilirubin, Calcium, Carbon Dioxide, Creatinine, Chloride, Glucose, Potassium, Protein, Sodium, and Urea Nitrogen
- 4 T3, free T4, TSH to be performed at screening and every 9 weeks (every third cycle) while on treatment
- 5 Pregnancy test must be done at screening and within 72 hours of starting study treatment for all women of childbearing potential and repeated as clinically indicated. Serum or urine tests may be used. If urine pregnancy is positive, confirm with serum.
- 6 If the patient consented to the optional testing and tissue is available (either from archival tissue or fresh biopsy tissue), PD-L1 analysis will be performed at central lab. If fresh tissue is being used, it should be obtained during screening window prior to study treatment. See section 15.
- 7 If clinically indicated, and not previously performed, tumor mutation burden analysis will be performed at central lab. If performed, results should be collected for the study. See section 15.
- 8 Patients must have existing Ki-67 results from archival tissue or available tissue for Ki-67 testing. If no archival tissue is available the subject must agree to a fresh biopsy for testing to qualify for the study. Ki-67 analysis will be performed at local lab if not previously performed. See section 15.
- 9 ECG will be done if medically indicated
- 10 CT of the abdomen/chest/pelvis must be repeated every 6 weeks through C12 (36 weeks), then every 12 weeks until disease progression. Progression must be confirmed no earlier than 4 weeks and no later than 8 weeks. Scans must be completed within 7 days prior to the next dosing cycle.
- 11 Pembrolizumab 200 mg IV q3weeks
- 12 Follow-up should occur no less than every 6 months for 4 years following study enrollment
- 13 Baseline procedures do not need to be repeated if screening procedures have been done within 7 days of start of treatment
- 14 MRI may be required at baseline for subjects with previously treated brain metastases

## 10 STUDY PROCEDURES

### 10.1 Screening Evaluations

- Informed Consent
- Physical examination with vital signs and ECOG Performance Status
- Review of medical history/baseline symptoms
- Review baseline concomitant medications
- Laboratory assessments:
  - CBC with differential
  - CMP to include sodium, potassium, chloride, carbon dioxide or bicarbonate, blood urea nitrogen (BUN), creatinine, glucose, total protein, albumin, calcium, AST, ALT, alkaline phosphatase, total bilirubin
  - Coagulation to include PT/INR and aPTT
  - Thyroid function tests to include TSH, total T3, and free T4
  - Serum or urine pregnancy test (for women of childbearing potential) within 72 hours of starting study treatment
  - Urinalysis
- 12-lead ECG if clinically indicated
- CT scans and disease assessments for baseline irRECIST
- MRI only for subjects with previously treated brain metastases
- Archival tissue or fresh tissue biopsy (if archival tissue is not available) for Ki-67 testing (see footnote #8 in calendar)
- Archival tissue or fresh biopsy for central PD-L1 analysis if patients consent to optional testing.

### 10.2 On-Treatment Evaluations (every three weeks unless otherwise noted)

- Physical examination with vital signs and ECOG Performance Status
- Laboratory assessments (do not need to be repeated if screening labs were performed within 7 days of C1D1):
  - CBC with differential
  - CMP to include sodium, potassium, chloride, carbon dioxide or bicarbonate, blood urea nitrogen (BUN), creatinine, glucose, total protein, albumin, calcium, AST, ALT, alkaline phosphatase, total bilirubin
  - Coagulation to include PT/INR and aPTT
  - Thyroid function tests to include TSH, total T3, and free T4 *at the beginning of every third cycle (C4D1, C7D1, C10D1, etc.)*
  - Serum or urine pregnancy test (for women of childbearing potential) *only on C1D1 if not performed during screening and within 72 hours of C1D1. Testing during treatment is required as clinically indicated*
- Safety assessment: monitoring and recording of all adverse events and serious adverse events.
- Review of concomitant medications

- CT scans and review of response every 6 weeks through C12 (36 weeks), then every 12 weeks until disease progression.
- Treatment with pembrolizumab 200 mg

### **10.3 End of Treatment Assessments:**

- Physical examination with vital signs and ECOG Performance Status
- Laboratory assessments:
  - CBC with differential
  - CMP to include sodium, potassium, chloride, carbon dioxide or bicarbonate, blood urea nitrogen (BUN), creatinine, glucose, total protein, albumin, calcium, AST, ALT, alkaline phosphatase, total bilirubin
  - Thyroid function tests to include TSH, total T3, and free T4 *at the beginning of every third cycle (C4D1, C7D1, C10D1, etc.)*
  - Urinalysis
- Safety assessment: monitoring and recording of all adverse events and serious adverse events.

### **10.4 Follow-up Assessments**

After coming off treatment patients will be followed per standard of care practice for progression free survival. For patients who come off trial prior to disease progression, disease assessments should continue every 12 weeks. Follow-up should occur no less than every 6 months for 4 years following study enrollment.

## **11 CRITERIA FOR EVALUATION AND ENDPOINT**

### **11.1 Efficacy**

Disease assessments will be measured by CT or MRI scan and assessed according to Immune related RECIST (irRECIST) based on Nishino et. al. (21)

Response rate is the primary response objective. Generally, evaluable patients should have baseline scans and one 6 week follow-up scan to be evaluable for response assessment. Patients should also have received at least 2 cycles of Pembrolizumab to be considered evaluable for response.

#### **11.1.1 irRECIST**

Measurable disease/non-measurable and target/non-target criteria- using one-dimensional measurements (simulating RECIST 1.1):

The following definitions and criteria (irRECIST) should be used for the baseline evaluations of existing disease, and for the ongoing evaluation of tumor measurements according to Nishino, an adaptation of Wolchok (22).

**Measurable lesions** - lesions that can be accurately measured in at least one dimension with longest diameter (LD)  $\geq$  10 mm using CT, MRI, or caliper measurements or  $\geq$ 20 mm with x-

ray. Lymph nodes which are defined as measurable at baseline must meet the criterion of a short axis  $> 15\text{mm}$  by CT scan.

**Non-measurable lesions** - all other lesions including small lesions (LD  $< 10\text{ mm}$  with CT, MRI, or caliper measurements or  $<20\text{ mm}$  with x-ray).

**Target Lesions** - all measurable lesions, up to a maximum of **five lesions**, should be identified as *target* lesions to be measured and recorded on the medical record at Screening. The *target* lesions should be representative of all involved organs. In addition, *target* lesions should be selected based on their size (lesions with the longest diameters), their suitability for accurate repeat assessment by imaging techniques, and how representative they are of the patient's tumor burden. At screening, a sum of the products of diameters (SPD) for all *target* lesions will be calculated and considered the baseline sum of the products of diameters. Response criteria to be followed are listed below. The baseline sum will be used as the reference point to determine the objective tumor response of the *target* lesions at tumor assessment (TA).

**Non-Target Lesions** - measurable lesions, other than *target* lesions, and all sites of non-measurable disease, will be identified as *non-target* lesions. *Non-target* lesions will be recorded on the medical record and should be evaluated at the same assessment time points as the *target* lesions. In subsequent assessments, *non-target* lesions will be recorded as "stable or decreased disease," "absent," or "progression."

**New Lesions and non-target lesions** - In irRECIST a new lesion does not automatically indicate progressive disease

New measurable lesions are added to the sum of the longest diameters of the previously existing target lesions, and the sum of the longest diameters is followed at each subsequent tumor assessment

New measurable lesions are defined using the same criteria as for baseline target lesions in RECIST 1.1. New measurable lesions shall be prioritized according to size and the largest lesions shall be selected as new measured lesion up to 2 lesions per organ and 5 new lesions total.

Non-target lesions (baseline and new non measurable) are used for determination of Complete Response. The RECIST 1.1 definitions for the assessment of non-target lesions apply.

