### 5.1 Inclusion Criteria

**Yes/No (Response of "no" = patient ineligible)**

**5.1.1** \_\_\_\_\_ Histologically confirmed, metastatic or unresectable neuroendocrine carcinoma of non-pulmonary origin, high grade as indicated by Ki-67 >20% and/or > 20 mitoses/10 hpf. Patients must have existing Ki-67 results from archival tissue or available tissue for Ki-67 testing. If no archival tissue is available the subject must agree to a fresh biopsy for testing to qualify for the study.

**5.1.2** \_\_\_\_\_ Patients must have progressed during or after first-line treatment for metastatic or unresectable disease with either a platinum-based regimen (e.g. carboplatin + VP16, cisplatin + VP-16, FOLFOX) OR temozolomide-based regimen. Patients must have failed at least one line of therapy but no maximum number of therapies is exclusionary (i.e. second-line therapy and beyond).

**5.1.3** \_\_\_\_\_ Have measurable disease based on irRECIST.

**5.1.4** \_\_\_\_\_ Be  $\geq$  18 years of age on day of signing informed consent.

**5.1.5** \_\_\_\_\_ Have a performance status of 0 or 1 on the ECOG Performance Scale.

**5.1.6** \_\_\_\_\_ Demonstrate adequate organ function as defined in Table 2, all screening labs should be performed within 14 days of treatment initiation.

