**5.1.11** \_\_\_\_\_ Must have recovered from adverse effects of any prior surgery, radiotherapy or other antineoplastic therapy.

**5.1.12** \_\_\_\_\_ Last dose of any antineoplastic therapy  $\geq 2$  weeks (including chemotherapy, small molecule inhibitors, radiation, and/or other investigational anticancer agents). Patients receiving hormone manipulation (e.g. SERMs, aromatase inhibitors, LHRH agonist, etc.) for reasons other than treatment of metastatic breast cancer may continue this treatment at the discretion of the investigator.

**5.1.13** \_\_\_\_\_ Able to provide informed consent and willing to sign an approved consent form that conforms to federal and institutional guidelines.

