## **5.2 Exclusion Criteria**

### **Yes/No (Response of “yes” = patient ineligible)**

**5.2.1**  Is currently participating and receiving study therapy or has participated in a study of an investigational agent and received study therapy or used an investigational device within 2 weeks of the first dose of treatment.

**5.2.2**  Has a diagnosis of immunodeficiency or receiving steroid therapy of any other form of immunosuppressive therapy within 7 days prior to first dose of trial treatment. Subjects who receive daily steroid replacement therapy serve as an exception to this rule. Daily prednisone at doses of 5 to 7.5 mg (or hydrocortisone equivalent doses) is an example of replacement therapy.

**5.2.3**  Has a known history of active TB (Bacillus Tuberculosis).

**5.2.4**  Hypersensitivity to pembrolizumab or any of its excipients.

**5.2.5**  Has had a prior anti-cancer monoclonal antibody (mAb) within 4 weeks prior to study Day 1 or who has not recovered (i.e.,  $\leq$  Grade 1 or at baseline) from adverse events due to agents administered more than 4 weeks earlier.

**5.2.6**  Has had prior chemotherapy, targeted small molecule therapy, or radiation therapy within 2 weeks prior to study Day 1 or who has not recovered (i.e.,  $\leq$  Grade 1 or at baseline) from adverse events due to a previously administered agent. Note: Subjects with  $\leq$  Grade 2 neuropathy are an exception to this criterion and may qualify for the study. Note: If subject received major surgery, they must have recovered adequately from the toxicity and/or complications from the intervention prior to starting therapy. Patients receiving hormone manipulation (e.g. tamoxifen, aromatase inhibitors, LHRH agonist, etc.) for reasons other than treatment of metastatic breast cancer may continue this treatment at the discretion of the investigator.

**5.2.7**  Has a known additional malignancy that is progressing or requires active treatment. Exceptions include basal cell carcinoma of the skin or squamous cell carcinoma of the skin that has undergone potentially curative therapy or in situ cervical cancer. Patients on long-term adjuvant therapy with no evidence of disease are not excluded if felt appropriate by investigator.

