### **Response Categories:**

- **Complete Response (irCR):** disappearance of all not-nodal target lesions and non-target lesions in two consecutive observations not less than 4 weeks apart. In addition, any pathological lymph nodes assigned as target lesions must have a reduction in short axis to  $<10\text{mm}$  (sum of diameters may be greater than zero at the time of CR, if nodal lesion are including as target lesions).
- **Partial Response (irPR):** at least a 30% decrease in the sum of diameters of all target lesions including new target lesion in two consecutive observations not less than 4 weeks apart, taking as reference the baseline sum of diameters.

- **Progressive Disease (irPD):** at least a 20% increase in the sum of diameters of all measured target lesions including new measurable lesions. The reference for irPD will be the smallest sum of diameter of all target lesions recorded at original baseline or subsequent. Progression must be confirmed with a follow up scan no less than 4 weeks and no more than 8 weeks after the first scan that shows disease progression.
- **Stable Disease (irSD):** neither a sufficient shrinkage to qualify of irPR or irCR, or an increase in the sum of target lesions which would qualify for irPD.

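### Lesions irradiated before entry can be target lesions with no condition attached, so a size change caused by radiotherapy enters the sum that decides irPR

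*Combined protocol and SAP*

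**What the plan says.** **Target lesions (11.1.1).** The starting set is "all measurable lesions, up to a maximum of" five. On how to choose, the section says that target "lesions should be selected based on their size (lesions with the longest diameters"), and adds "their suitability for accurate repeat assessment by imaging techniques, and how representative they are of the patient's tumor burden". It also asks that the targets represent all involved organs.

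**Measurability (11.1.1).** This is a matter of dimension only: "lesions that can be accurately measured in at least one dimension with longest diameter (LD") at or above a stated minimum, with a short-axis rule for nodes. Prior treatment of the lesion is not mentioned.

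**Entry (5.1.3).** The criterion reads "Have measurable disease based on irRECIST". It does not ask that the lesion be unirradiated or have grown since irradiation.

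**Radiotherapy before entry.** Exclusion 5.2.6 covers a patient who "Has had prior chemotherapy, targeted small molecule therapy, or radiation therapy within 2 weeks prior to study Day 1". Inclusion 5.1.12 sets the same minimum of 2 weeks since the last antineoplastic therapy, "including chemotherapy, small molecule inhibitors, radiation, and/or other investigational anticancer agents". Radiotherapy earlier than that is allowed.

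**Response (11.1.1, Response Categories).** irPR is "at least a 30% decrease in the sum of diameters of all target lesions", new ones included, on two consecutive observations at least 4 weeks apart, relative to baseline. The cause of the decrease plays no part.

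**The concern.** A patient may finish radiotherapy to a large lesion a little over 2 weeks before Day 1. If the patient has five or fewer measurable lesions, 11.1.1 calls for that lesion to be a target. If there are more, ranking by size may still favour it. Should the lesion go on shrinking after Day 1 because of the radiotherapy, the target sum falls and the fall is credited to pembrolizumab. This can happen even when the baseline scan follows the last fraction and no radiotherapy is given on study.

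Overall response rate is the primary endpoint and there is no control arm, so nothing in the data separates residual radiotherapy effect from drug effect. The decision rule turns on small counts: 2 responses in 13 open stage 2, and 6 in 34 reject the null. A few misattributed responses could affect either step.

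**Working it through.** **1. The plan's own design.** Inputs from section 12: null rate 10%, alternative 25%, alpha 0.10, beta 0.20; 13 patients in stage 1, continue with 2 or more responses, 21 more, reject with 6 or more of 34.

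P(reject | p) = sum over x = 2 to 13 of Bin(x; 13, p) × P(Y ≥ 6 − x), with Y ~ Bin(21, p).

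- At p = 0.10: 0.0957, within the 0.10 limit.
- At p = 0.25: 0.811, above the 0.80 target.

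A grid search for the Simon optimum returns the same design, so the stated figures reproduce.

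**2. When one irradiated lesion gives irPR alone.** Let w be its share of the baseline sum, with the other targets unchanged and no new measurable lesion. The shrinkage needed is 0.30 / w.

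| Share w | Shrinkage needed |
|---|---|
| 100% | 30% |
| 75% | 40% |
| 60% | 50% |
| 50% | 60% |
| 30% | 100% |

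Below a 30% share it cannot do so alone.

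**3. Worked examples.** The targets are 50 mm (irradiated) and 30 mm (not), a sum of 80 mm.

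- False response: the 50 mm lesion halves and the other is unchanged. Sum 25 + 30 = 55 mm; (80 − 55)/80 = 31.25% decrease, which is irPR if confirmed.
- Near miss: as above, but the untreated lesion grows by 2 mm. Sum 25 + 32 = 57 mm; 23/80 = 28.75% decrease, not irPR.
- Masked response: the irradiated mass does not change and the untreated lesion halves on drug. Sum 50 + 15 = 65 mm; 15/80 = 18.75% decrease, scored irSD.

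**4. Effect on the decision rule.** The documents give no frequency of prior radiotherapy, so both inputs are assumed: s, the share of patients affected (2-10%), and q, the chance that radiotherapy alone turns a drug non-responder among them into a confirmed irPR (10-30%). Only non-responders can be converted, so at a true rate of 10%:

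scored rate = 0.10 + 0.90 × s × q.

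| s | q | Scored rate | P(reject) |
|---|---|---|---|
| 0 | – | 10.0% | 0.096 |
| 2% | 10% | 10.2% | 0.102 |
| 5% | 30% | 11.4% | 0.149 |
| 10% | 20% | 11.8% | 0.169 |
| 10% | 30% | 12.7% | 0.213 |

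In counts, the expected number of false responses among 34 patients is 34 × 0.90 × s × q. That is 0.06 at the low end (34 × 0.90 × 0.02 × 0.10) and 0.92 at the high end (34 × 0.90 × 0.10 × 0.30). These figures model false responses only and make no offset for masked ones.

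**The case against.** **The text does not force the choice.** A reader might infer that every measurable lesion must be a target. The wording is should, the set is capped at five, and representativeness is a criterion. With more than five measurable lesions an irradiated one may be left out. This stands, but with five or fewer the text does call for including it.

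**The bias has two directions.** A reader might infer that the gap can only favour the drug. The masked-response example shows otherwise, and the documents do not settle the net direction. False responses remain the main concern because they raise the chance of declaring activity in a trial with no control.

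**A false irPR is hard to reach.** It needs a dominant irradiated lesion, large shrinkage, little growth elsewhere and no appreciable new measurable disease, across two scans, in patients who have already progressed on earlier treatment. This stands, and it argues for the lower part of the assumed range. Confirmation guards against measurement error, however, not against lasting radiotherapy shrinkage. Progression under 5.1.2 can be at any site and at any earlier time, so it does not show that the irradiated lesion grew after irradiation.

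**Other provisions may cover it.** Exclusion 5.2.12 lets the investigator exclude a patient whose earlier therapy might confound results, but it acts on patients, not lesions, and is discretionary. Brain lesions, the irradiated site the protocol discusses most (5.1.7, 5.2.8), would not normally be followed, since section 9 schedules CT of chest, abdomen and pelvis and mentions MRI only at baseline. Other sites remain open.

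**The cited criteria may contain a rule.** Section 11.1.1 follows a cited irRECIST publication and says it simulates RECIST 1.1. Whether either restricts irradiated lesions cannot be checked from these documents. The protocol writes out its own target-lesion rules and includes no such restriction.

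**Conclusion.** The gap is clear on the text: nothing in 11.1.1 or elsewhere sets a lesion-level condition for disease irradiated before entry, and the size of such a lesion counts toward the primary endpoint. How much it matters is uncertain. On the assumed ranges, P(reject) at a true 10% rate runs from 0.10, barely above the design's 0.096, to 0.21, about twice the planned limit. This rests on s and q, neither of which the documents inform.

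Two stronger readings are not supported. Adding s × q directly to 10% (10% affected, 20-30% converted, hence 12-13%) would count patients who already respond to the drug; limiting conversion to non-responders gives 11.8-12.7%. Nor do the documents show that a new eligibility limit in 5.1.3 is needed. Section 2.4 describes a relatively rare population, and a rule at lesion level addresses the main problem.

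The change is worth making because it is cheap and protects the primary endpoint. The evidence does not show that the trial's conclusion would be wrong without it.

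**What to change.** Add to 11.1.1, under Target Lesions: a measurable lesion irradiated before entry is recorded as non-target unless it has shown documented growth on imaging since that radiotherapy.

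The rule leaves one case open: a patient whose only measurable lesion was irradiated and has not since grown. In place of a new limit in 5.1.3, the protocol could optionally keep such a patient, allow that lesion to be measured, and record the prior-radiotherapy status of every target lesion. ORR would then be reported with and without patients whose only measurable disease was irradiated.

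The two-stage design does not change: 13 then 21 patients, alpha 0.0957, power 0.811. The cost is slightly more recording of lesion history at screening, and fewer target lesions in a few patients.
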